Co-ordinating investigator	A Co-ordinating Investigator is the investigator that coordinates the investigators and/or activities nationally.		
LDL	Low-density lipoprotein		
LDL-C	Low-density lipoprotein cholesterol		
LOCF	Last observation carried forward		
mg	Milligram		
mg/dL	Milligram per decilitre		
MI	Myocardial infarction		
mL	Millilitre		
NCEP	National Cholesterol Education Program		
Non-HDL-C	Non-high-density lipoprotein cholesterol		
OCT	Oral contraceptive therapy		
OAE	Other Significant Adverse Event (i.e., adverse events of particular clinical importance, other than SAEs and those AEs leading to discontinuation of the patient from study treatment; see definition in Section 4.8.1.1).		
Outcome variable	A variable (usually a derived variable) specifically defined to be used in the analysis of a study objective.		
PD	Pharmacodynamic		
PI	Prescribing Information		
РК	Pharmacokinetic		
PP	Per-protocol		
Principal investigator	A person responsible for the conduct of a clinical study at an investigation study site. Every investigational study site has a principal investigator.		
SAP	Statistical analysis plan		
SAS	Statistical Analysis System [®]		
SAE	Serious adverse event (see definition in Section 4.8.1.1).		
SD	Standard deviation		
SGOT	Serum glutamic oxaloacetic transaminase (=AST)		
SGPT	Serum glutamic pyrivic transaminase (=ALT)		
ST	Study team		
Statin naïve	Patients will be considered statin naïve if they had, at least, 6 month or more without taking any statin treatment prior to visit 1.		
TC	Total cholesterol		
TG	Triglycerides		

Clinical Study Protocol Drug Substance Rosuvastatin Study Code DM-CRESTOR-0002 Edition Number 2.1 Date 28-March-2007

Abbreviation or special term	Explanation
TIA	Transient Ischaemic Attack
TLC Diet	Therapeutic Lifestyle Changes Diet
TSH	Thyroid-stimulating hormone
ULN	Upper limit of normal
SDV	Source data verification
VLDL	Very-low-density lipoprotein
VLDL-C	Very-low-density lipoprotein cholesterol

1. INTRODUCTION

1.1 Background

Hypertriglyceridemia (HTG) has been lately recognized as an independent factor for cardiovascular disease (CVD), regardless LDL-C levels(1). HTG is a component of the so-called Metabolic Syndrome (MS) along with the reduction in high density lipoprotein cholesterol (HDL-C) levels(2,3). MS is a mayor risk factor for diabetes -that in turn is a mayor risk factor of CVD -and it is recognized also as a mayor risk factor for CVD itself (2,4). It also seems that the most common dislipidemia in diabetes are HTG, low serum levels of HDL-C and an increase in the serum fraction of small dense low density lipoprotein cholesterol (LDL-C) particles(5). Serum LDL-C elevation is some times present, but is not a criteria of the metabolic syndrome.

The mechanisms by witch TGs are involved in CVD are not well establish, nevertheless, it seems it has to do with the atherogenic process. There is now some evidence that points that HTG comes along with LDL-C small dense particles (sd-LDL-C) (6). Small dense LDL particles have been suggested to be highly atherogenic due the higher penetration into the arterial wall, their low binding affinity for the LDL receptor, their prolonged plasma half-life, and their lower resistance to oxidative stress compare to that of larger LDL(7). A recent report of the Québec cardiovascular study has confirmed that predominance sd-LDL is a strong and independent predictor factor for CVD during the first 7th years of follow-up(8).

In Mexico, the prevalence of MS and Diabetes had been increasing in an alarming way. There are around 6.5 million people with diabetes and as a country Mexico will pass from the 9th place in the world to the 7th place in 2025 in diabetes prevalence(24). From 1940 mortality due to diabetes has raised from 5 to more than 50/100,000 habitants (aprox 6 death per hour)(9, 10). During 2005, diabetes was the first cause of general mortality(11). Diabetes has been associated with HTG and low HDL-C levels. In Mexico more than 65% of diabetic population had HTG and more than 60% had low HDL-C which was significantly more than the 31-50% and 33-39% that had the non diabetic population respectively(9).

Talking about prevalence of MS is quite more difficult. It will depend on the definition use to make the diagnosis. Nevertheless, Aguilar-Salinas *et al.* made an estimation of prevalence using WHO and NCEP ATP III criterion and found that in Mexico age-adjusted prevalence was 13.61% for WHO criteria and 26.6% for the ATPIII definition. Prevalence was 9.2 and 21.4%, respectively, in subjects without diabetes. Thirty five percent of affected cases were >40 years old(12).

In a different analysis, Barquera, *et al.* found that the most common dislipidemia in Mexican population are hipoalfalipoproteinemia (HDL-C <40mg/dl) and HTG (TG>150 mg/dl). The probability of the association of low HDL-C; HTG and hypercholesterolemia is 0.080 in general population, and it rises up to 0.16 when it is associated to obesity (13).

1.2 Rationale for this study

Currently the treatments for HTG are fibrates. Although the FIELD trial proved that fenofibrate could reduce total CV events (due to myocardial infarcts and revascularization), it fails to reduce the risk of the primary outcome of coronary events (14). Other trials have demonstrated that fenofibrates can reduce significantly TG levels (-37%), but they increase LDL-C levels. It seems fenofibrates can reduce the sd-LDL and increase the larger LDL, reducing atherogenic lipid profile (15). Actually, the NCEP ATPIII guidelines recommend to first lower LDL-C levels before TG levels, especially in patients with high risk (as diabetics) to levels below 100 mg/dl or even to levels below 70 mg/dl (2, 3).

Rosuvastatin has proven to reduce LDL-C -45 to -50% in many controlled trials (16-19) and TG from -21 to -37% (20, 21); while increasing HDL-C between 7 to 10% (18-19).

For this reason, assuming that CV risk is a sum of factors that includes high LDL-C (or not so high sd-LDL), HTG and low HDL-C; modifying the whole atherogenic lipid profile will reduce CV risk in our hypertriglyceridemic patients. The rational for this study is based on the assumption that rosuvastatin will provide the necessary reduction of triglycerides and at the same time, will reduce LDL-C reducing the risk of CVD.

2. STUDY OBJECTIVES

2.1 **Primary objective**

The primary objective of this study is to evaluate the efficacy of rosuvastatin in reducing triglycerides levels in hypertriglyceridemic Mexican patients from baseline to week 8.

2.2 Secondary objectives

The secondary efficacy objectives of the study are as follows:

- 1. To evaluate the efficacy of RSV from baseline to week 8 on:
 - a. Non-HDL-C levels
- 2. To evaluate the efficacy of RSV from baseline to week 8 on
 - a. Low-density lipoprotein cholesterol (LDL-C)
 - b. Total cholesterol (TC)
 - c. High-density lipoprotein cholesterol (HDL-C)
 - d. Apolipoprotein A1 (ApoA-1), apolipoprotein B (ApoB) and
 - e. TC/HDL-C, LDL-C/HDL-C, nonHDL-C/HDL-C and ApoB/ApoA-1 indexes.
- 3. To determine the efficacy of RSV in reducing high-sensitive C- reactive protein (hsCRP) from baseline to week 8.

The secondary safety objective of this study is:

• To evaluate the effect of RSV on the incidence and severity of adverse events and laboratory data

3. STUDY PLAN AND PROCEDURES

3.1 Overall study design and flow chart

This is an 8 week, randomised, double blind, double dummy, national, multicentre study with 3 parallel treatment groups: rosuvastatin 10 mg, rosuvastatin 20 mg and placebo. The primary end point of the study is the change in triglycerides levels from baseline to week 8. Approximately 10 to 12 centres will be required in order to recruit 330 randomised patients, of whom 285 to 300 are expected to be fully evaluable (i.e., to allow for approximately 10 to 15% of randomised patients being non-evaluable). The approximate numbers of randomised patients will be recruited from Mexico City (150 patients), Monterrey (90 patients), Guadalajara (60 patients), Toluca (30 patients) and San Luis Potosi (30 patients). It is anticipated that in order to achieve this number of randomised patients, approximately 990 patients will need to enter the lead-in period of the study (screen failure rate 3:1). Centres will be required to randomise approximately 30 patients each. Centres may be discontinued from the study if recruitment rates are poor and new centres may be added if necessary to achieve recruitment goals. Recruitment will be competitive across cities and centres (thus, centres numbers are approximate). There is no maximum number of patients that centres can recruit. and centres will stop enrolment once enough patients are screened to provide the projected number randomised.

There are 4 clinic visits planned. Visit 1 and 2 occurs during the lead-in period. Visit 2.1 is the randomisation visit, and Visit 3 occurs during the randomised treatment period, is the final visit. For visit 1, the allowed window will be ± 3 days, for visit 2 the allowed visit window will be ± 3 days. For visit 2.1 the allowed visit window will be ± 2 day and for visit 3 the allowed visit window will be ± 3 days.

Male and female patients aged ≥ 18 with hypertriglyceridemia (HTG) and statin naïve (as defined by protocol) will be recruited. Patients will then enter a 4-week lead-in period during which they will undergo TLC dietary advice (see Appendix F) and no lipid lowering therapy will be allowed. All eligible patients will be randomised in a 1:1:1 ratio to receive ether rosuvastatin 10 or 20 mg/day or placebo once a day. Patients will be followed for 8 weeks. All patients will be offered the opportunity to continue with active commercially available therapy with rosuvastatin once the protocol is complete.

Visit 1. Dietary lead-in period (week -5)

- 1) Provision of written informed consent.
- 2) Medical History including complete physical examination, anthropometrics and vital signs, weight, height, body mass index (BMI) and abdominal circumference.
- 3) Eligible Criteria
 - a) Male and female subjects aged ≥ 18 years
 - b) Statin naïve patients (as defined by protocol)

- c) Without previous lowering lipid treatment other than statins 6 months before visit 1.
- d) Fasting TG concentrations at visit 1 of: $\geq 200 \text{ mg/dL}$ and $\leq 800 \text{ mg/dL}$.
- e) Fasting LDL-C \geq 100mg/dL and \leq 190 mg/dL at visit 1

(**Note:** the results of the above laboratory sample will not be available at visit 1 to make the eligibility decision. Therefore, if the subject's medical history meets the eligibility criteria the subject can enter into the dietary lead-in period of the study. However, when the laboratory results are available, if the results do not meet the above criteria, the subject should be contacted and discontinued from the study)

- f) Subjects willing to follow all study procedures including the attendance at clinics for scheduled study visits, fasting prior to clinic visits (Visits 1, 2 and 3 blood draws) and compliance with study treatment regimen.
- 4) Therapeutic Life Stile Change (TLC) advisory (see Appendix F)
- 5) Record of concomitant medication
- 6) Laboratory samples (see table 1)
- 7) Patients who do not meet the entry criteria should be considered screen failure and a screen failure CRF should be completed.

Visit 2. (Week -1)

Visit window allowed is \pm 3 days. To continue in the study, patients should fulfil the following criterion:

- 1. Fasting TG \geq 200 mg/dL and < 800mg/dL at visit 1.
- 2. Fasting LDL-C \geq 100mg/dL and \leq 190 mg/dL at visit 1
- 3. TLC advisory
- 4. Complete physical examination including anthropometrics and vital signs
- 5. Laboratory samples (see table 1)
 - a) Fasting TG \geq 200 mg/dL and < 800mg/dL at visit 2.

(Note: the results of the above laboratory sample will not be available at visit 2 to make the eligibility decision. Therefore, subjects will be randomised at visit 2.1, one week after visit 2, when the laboratory results are available. If the results do not meet the above criteria, the subject will be contacted and discontinued from the study)

- 5. Record of Adverse Events
- 6. Record of concomitant medication

Visit 2.1. Randomisation (Week 0)

Visit window allowed is ± 2 day. During this visit, laboratory results of the prior visit will be available and patients fulfilling the inclusion criterion will be randomised.

- 1. Fasting TG \geq 200 mg/dL and < 800mg/dL from visit 2.
- 2. Fasting LDL-C \geq 100mg/dL and \leq 190 mg/dL at visit 2.
- 3. Record of adverse events
- 4. Study drug will be dispensed in this visit.
- 5. Record of concomitant medication

[figure not shown]
Visit 3. Final (Week 8)

Visit window allowed is ± 3 days. Visit 3 will occurred after 8 weeks of following patients with treatment. This will be the final visit.

- 1. TLC advisory
- 2. Complete physical examination including anthropometrics and vital signs
- 3. Laboratory samples (see table 1)
- 4. Record of adverse events
- 5. Record of concomitant medication
- 6. Study drug will be recovered in this visit. Tablets will be counted and noted for assessing compliance.
- 7. All patients will be offered the opportunity to continue with active commercially available therapy with rosuvastatin, according to the expert opinion of investigator, once the protocol is complete.

Clinical Study Protocol Drug Substance Rosuvastatin Study Code DM-CRESTOR-0002 Edition Number 2.1 Date 28-March-2007

Figure 1 Study flow chart

RSV: rosuvastatin

Clinical Study Protocol Drug Substance Rosuvastatin Study Code DM-CRESTOR-0002 Edition Number 2.1 Date 28-March-2007

Table 1 **Study Plan**

Week	-5	-1	0	8
Visit	1	2	2.1 ⁿ	3
Visit window		± 3 days	±2 day	± 3 days
Informed consent ^a	✓			
Dietary counselling	✓		✓	✓
24 hrs diet recall	✓		✓	✓
Medical history/demography	✓			
Concomitant medication	✓ b	✓	✓	✓
Physical examination ^c	✓ ^d	✓		✓
Vital signs	✓	✓		✓
Eligibility criteria ^e	✓	✓	✓	
Randomization			✓	
Fasting lipid profile ^f	✓	✓		✓
Apolipoproteins ^g		✓		✓
TSH	✓			
Glucose	✓	✓		✓
HbA _{1c}	✓			
Urinalysis ^h		✓		✓
Reduced hepatic profile ^j	✓			
Complete hepatic profile ^k		✓		✓
Urea	✓	✓		✓
Creatinine	✓	✓		✓
СК	✓	✓		✓
β-HCG ¹	✓			
hsCRP		✓		✓
Adverse events ^m		✓	✓	✓
Study drug dispensing			✓	
Study drug compliance and accountability				~

^a Informed consent will be taken at or before Visit 1, before any study related procedures are performed ^b Prior medications to be collected at Visit 1

^c Weight and waist circumference will be measured at Visits 1, 2 and 3. Height will additionally be measured at Visit 1

^d Review and titrate if necessary patient's anti-hypertensive medication, to an individually optimised dose to a blood pressure target of <130/80 mmHg based JNCVII guidelines and investigator discretion.

^e Patients should fulfil all inclusion criterion with no exclusion criterion to continue in the study during visit 1, 2 and 2.1.

^f Lipid profile: TG, LDL-C, TC, HDL-C, nonHDL-C, TC/HDL-C, LDL-C/HDL-C and non-HDL-C/HDL-C ^g Apolipoprotein analysis to include ApoA-1, ApoB, ApoB/ApoA-1 ratio

^h Urinalysis will consist of: visual description (colour and appearance), a dipstick test (specific gravity, pH, protein (qualitative), haematuria, glucose, ketones, bilirubin and blood), microscopy (red blood cells, white blood cells, bacteria, casts and crystals.

^j Reduced hepatic profile will consist of: ALT, AST and GGT

^k Complete hepatic profile will consist of: total bilirubin, ALT, AST, alkaline phosphatase and gamma-glutamyl transferase (GGT)

¹An assay of B-HCG will only be performed at visit 1 for women of childbearing potential.

^m SAEs should be followed up for 30 days after the last dosing of study treatment

ⁿ Patients will be randomised once the laboratory results from visit 2 are available. Study drug will be dispensed at visit 2.1.

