3.2 Rationale and risk/benefit assessment

3.2.1 Rationale for study design and control group

The NCEP ATPIII recommendations for patients with HTG are first to lower the LDL-C levels and then the TG levels in order to reduce the CV risk(2). In HTG patients, a drug that can reduce both parameters will have an additional benefit.

Statins have been shown convincingly to reduce cardiovascular morbidity and mortality in multiple large outcomes trials in various populations, with substantial reductions in LDL-C and TG levels in non-diabetic and diabetic patients (22, 23). Statins reducing TG levels are known to be directly related to the LDL-C reduction potency meaning that more potent statins should be more effective in lowering TG. For this reason, the current study will use one of the most potent statins (RSV) and will test its efficacy in reducing TG levels in Mexican HTG patients.

This study is using a placebo arm as a control. Patients that are currently on statin therapy cannot enter the study because it would not be ethic to stop their statin therapy. As we are using a placebo arm, the study will only last for 8 weeks and all patients will be treated with TLC diet as appropriate. After completing the study period, all patients will be offer to continue with active commercially available therapy determine by the investigator experience.

The 5-week lead in period will serve as a washout period of possible residual effects of preexisting lipid lowering therapy (other than statins) use, which is important to establish a reliable baseline to determine the change from baseline during double-blind treatment.

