3.3.5 Discontinuation of patients from treatment or assessment

3.3.5.1 Criteria for discontinuation

Patients may be discontinued from study treatment and assessments at any time. Specific reasons for discontinuing a patient from this study are:

- Voluntary discontinuation by the patient who is at any time free to discontinue their participation in the study, without prejudice to further treatment
- Safety reasons as judged by the investigator and/or AstraZeneca
- Occurrence of an adverse event, which in the opinion of the investigator warrants the patient's discontinuation. Patients who are discontinued from the study for non-serious or serious adverse events should be followed until the adverse event has been resolved or stabilised and no further change is expected
- If at any time, the patient experiences unexplained muscle pain, tenderness or weakness which is accompanied by CK>10 x ULN, study medication should be discontinued. See management of increased creatine kinase (CK) (Appendix E)
- If ALT (SGPT) is demonstrated to be 3 x ULN on two consecutive occasions >48 hours apart, without obvious reversible precipitating factors, withdrawal of study medication is recommended (see Appendix D)
- Severe non-compliance to protocol as judged by the investigator and/or AstraZeneca (any deviation from the protocol should be reported to the study team who will decide whether the patient should be discontinued from the study)
- Incorrect enrolment (screen failure) i.e., the patient was not randomised as does not meet the required inclusion/exclusion criterion
- Patient lost to follow-up
- Pregnancy
- Deterioration in the patient's condition which in the opinion of the investigator warrants study medication withdrawal.

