3.3.5.3 Procedures for discontinuation

Patients who discontinue should always be asked about the reason(s) for their discontinuation and the presence of any adverse events. If possible, they should be seen and assessed by an investigator(s). Adverse Events (AEs) should be followed-up. Serious Adverse Events (SAEs)

should be followed-up until resolution or until the patient is lost to follow-up. All investigational products should be returned to the clinic by the patient.

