4.8.2 Laboratory safety measurements and variables

4.8.2.1 Methods of assessment

Laboratory analysis will be performed at Visits 1, 2 and 3.

For visit 1, 20ml of blood will be needed. In this visit, lipid profile, glucose, HbA_{1c}, urea, creatinine, reduced hepatic profile (ALT, AST and GGT) and CK will be performed. A TSH analysis will be done and patients with levels ≥ 1.5 ULN will be excluded of the trial. β -HCG will be performed to women with childbearing potential at visit 1.

For visit 2 and 3, 10 ml of blood will be needed. In these visits, lipid profile, apolipoproteins, hsCRP, glucose, urea, creatinine, complete hepatic profile and CK will be performed.

A 10 mL mid-stream urine sample will be collected for analysis at the central laboratory at visits 2 and 3. It will consist of visual description (colour and appearance), a dipstick test (specific gravity, pH, protein (qualitative), haematuria, glucose, ketones, bilirubin and blood), microscopy (red blood cells, white blood cells, bacteria, casts and crystals.

In the event of elevated liver function tests, see Appendix D for guidance with regards to management of elevated liver enzymes.

In the case of new or increased symptoms of muscle pain/myopathy/elevation of CK to >5x ULN developing after randomisation, see Appendix E for guidance with regards to management of increased creatine kinase.

The volume of blood to be collected is detailed in section 4.9.

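### The only scheduled on-treatment ALT and CK fall at the final visit, the post-study offer is worded inconsistently and not related to those results, and early stoppers may give no post-baseline laboratory sample

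*Protocol*

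**What the plan says.** **Sampling.** Protocol section 4.8.2.1: "Laboratory analysis will be performed at Visits 1, 2 and 3". For Visits 2 and 3 it adds: "In these visits, lipid profile, apolipoproteins, hsCRP, glucose, urea, creatinine, complete hepatic profile and CK will be performed". The notes to Table 1 (section 3.1) say: "Study drug will be dispensed at visit 2.1". Visit 3 (week 8) is the final visit, and study drug is recovered there.

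**Withdrawal criteria.** Section 3.3.5.1 recommends withdrawing study drug on this condition: "If ALT (SGPT) is demonstrated to be 3 x ULN on two consecutive occasions >48 hours apart", provided there is no obvious reversible cause. Its CK criterion applies at any time and requires unexplained muscle symptoms together with CK above 10 x ULN.

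**Post-study offer.** The general text of section 3.1 says "All patients will be offered the opportunity to continue with active commercially available therapy with rosuvastatin", once the protocol is complete. Item 7 of Visit 3 repeats this and makes it subject to the investigator's expert opinion. Section 3.2.1 has, after the study period: "all patients will be offer to continue with active commercially available therapy determine by the investigator experience". Section 3.2.2 likewise speaks of an active treatment that the investigator decides on.

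**Availability of results.** The note to Visit 2 in section 3.1 says "the results of the above laboratory sample will not be available at visit 2 to make the eligibility decision", and places randomisation one week later for that reason. Nothing comparable is said for Visit 3.

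**Early stopping.** Of patients who discontinue, section 3.3.5.3 says: "If possible, they should be seen and assessed by an investigator(s". It names no laboratory sample. Section 3.3.5.2, by contrast, requires patients randomised in error and then taken off drug to complete the remaining visit and assessments.

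**The concern.** The protocol sets laboratory criteria for withdrawal, but its schedule gives one on-treatment reading, on the day treatment ends. Two things follow.

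First, the ALT criterion needs two readings, so during treatment it depends entirely on samples outside the schedule. A first raised value found at Visit 3 comes too late to affect study treatment. The decision still open at that point is what the patient takes next. The protocol describes that decision in differing terms and never says how it relates to the Visit 3 results or to a withdrawal criterion having been met.

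Second, the secondary safety objective in section 2.2 covers laboratory data, and section 6.2 names abnormal laboratory values as part of the safety outcome. Patients who stop early include those who stopped because of a reaction. If they give no sample after the first dose, the laboratory summaries describe mainly patients who tolerated eight weeks of treatment.

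**Working it through.** The protocol states no figure for this point, so there is none to reproduce. The check is a count of samples, a comparison of passages and a simple range.

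**1. On-treatment samples (Table 1, section 4.8.2.1).**
- ALT draws: weeks -5, -1, 8. CK draws: weeks -5, -1, 8.
- First dose: week 0.
- Draws after the first dose: ALT 1, CK 1, both at week 8, i.e. 8 x 7 = 56 days after dispensing. With the visit windows (2 days at Visit 2.1, 3 days at Visit 3) this is 56 - 5 = 51 to 56 + 5 = 61 days.

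**2. Against the criteria (section 3.3.5.1).**
- ALT: needs 2 consecutive values; scheduled on treatment 1; shortfall 2 - 1 = 1. A pre-treatment value does not help in a correctly enrolled patient, because exclusion criterion 11 removes ALT above 3 x ULN and the notes to Table 1 apply the criteria at Visits 1, 2 and 2.1. Even if an earlier value counted, the pair would be complete only at Visit 3, when drug is being recovered.
- CK: needs 1 value together with symptoms, at any time. A symptom-driven unscheduled sample can meet it.

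**3. The offer, side by side.**

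| Place | What is offered | Investigator's judgement stated? | Timing | Related to Visit 3 results or 3.3.5.1? |
|---|---|---|---|---|
| 3.1, general text | rosuvastatin, to all | no | protocol complete | no |
| 3.1, Visit 3 item 7 | rosuvastatin, to all | yes | protocol complete | no |
| 3.2.1 | active therapy | yes | study period completed | no |
| 3.2.2 | active treatment | yes | study period concluded | no |

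The passages differ on the product and on the investigator's role. None defines completion relative to the arrival of the Visit 3 results.

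**4. Patients who may lack a sample.**
- Section 6.5 expects 10 to 15% of 330 not to complete: 0.10 x 330 = 33; 0.15 x 330 = 49.5, about 50.
- Section 3.1 expects 285 to 300 evaluable patients: 330 - 300 = 30; 330 - 285 = 45. The two statements agree roughly.
- Of the 2 x 110 = 220 patients randomised to rosuvastatin, 220 x 0.85 = 187 to 220 x 0.90 = 198 would reach Visit 3 if the rate is the same in each arm (an assumption).
- Since no draw is scheduled between weeks 0 and 8, a patient who stops in between and is not sampled off schedule has no laboratory value after baseline.

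**The case against.** A reader might infer that the discontinuation rules cannot operate at all. The protocol does not support that. The CK criterion is triggered by symptoms at any time, section 4.9 foresees additional samples at unscheduled visits, and section 3.3.5.1 also allows discontinuation for adverse events and for safety as judged by the investigator or sponsor. A rule that asks for two values more than 48 hours apart presupposes a repeat taken when needed. Sections 3.3.5.1 and 4.8.2.1 refer raised liver tests and CK to Appendices D and E. Those are not in the text available here and may cover repeat testing, so missing confirmation guidance cannot be claimed. This part of the objection stands.

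A reader might also infer that rosuvastatin is offered before the Visit 3 results exist, and that a patient over a threshold leaves with the drug. The first is plausible: the same laboratory performs all analyses, the blood panel is the same at Visits 2 and 3, and Visit 2 results are not ready on the day. But the notes on availability concern eligibility at Visits 1 and 2, and the protocol is silent on Visit 3. The second is not directed by the text. The offer follows completion of the protocol and, in three of the four places, is left to the investigator's judgement. What can be said is that no passage excludes it.

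Finally, one on-treatment safety panel in an eight-week phase IV trial is a defensible design choice, and section 4.8.1.2 requires adverse events to be followed until resolved or stable. That answers any call for more visits. It does not answer the inconsistent offer, the undefined point of completion, or the difference between sections 3.3.5.2 and 3.3.5.3.

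**Conclusion.** The point holds in limited form.

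- **Schedule and ALT criterion:** one scheduled on-treatment value against a rule that needs two. During treatment the rule depends on unscheduled samples and possibly on Appendices D and E.
- **Offer:** three versions in four places, none related to the Visit 3 safety results or to section 3.3.5.1.
- **Early stoppers:** 33 to about 50 of 330 may have no post-baseline laboratory value. This is an upper range. It rests on the protocol's own 10 to 15% and on none of these patients being seen and sampled; those who are sampled reduce it. It would be wrong to say that early stoppers contribute nothing.

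It would also be wrong to say that all 220 patients randomised to rosuvastatin reach the offer: on the protocol's own rate, about 187 to 198 attend Visit 3. The point concerns the completeness of the laboratory safety data and the consistency of the text. It does not bear on the sample size calculation, and no view is taken here on which clinical rule is right.

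**What to change.** 1. Reconcile the four descriptions of the post-study offer (section 3.1 general text, section 3.1 Visit 3 item 7, and sections 3.2.1 and 3.2.2) with one another and with section 3.3.5.1. State what completion of the protocol means relative to receipt of the Visit 3 laboratory results. The content of the offer is for the sponsor and investigators to settle.
2. Align section 3.3.5.3 with section 3.3.5.2, so that patients who stop early and are seen have the laboratory assessments already planned for Visit 3.

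The first change costs wording only. The second costs one already planned blood draw, taken earlier, for at most the 33 to about 50 patients expected not to complete. Neither adds a threshold, a scheduled visit or a clinical rule.
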